5.3.2.1. Study 0918T0633

Study 0918T0633 was a Japanese non-controlled, open-label study conducted in pediatric subjects with influenza (either inpatient or outpatient) that ran from September 2009 to December 2009. A total of 117 subjects, aged ≥ 28 days to < 16 years, were enrolled of which the ITTI analysis set was 112. The study excluded children with significant comorbidities such as encephalopathy, epilepsy, chronic respiratory disorders, congestive heart failure, immunosuppression and renal failure. Subjects were treated with peramivir 10 mg/kg (maximum dose 600 mg) IV for up to 5 days. This dose was believed to provide children with an adult equivalent of 300 to 600 mg peramivir a day. Two subjects received 2 doses, and the rest received a single infusion. The primary endpoint was the median time to alleviation of influenza defined as mild to no cough or nasal discharge and normal body temperature. Overall the median time was 27.9 hours (95% CI 21.7-31.7) with no differences noted between the age groups of 28 days to < 2 years, 2 to < 6 years, 6 to < 12 years, and 12 to < 16 years of age. Normal temperature of < 37.5°C was recovered in a median time of 20.4 hours (95% CI 19.1-20.9). If all influenza symptoms, including cough, sore throat, headache, nasal discharge, fever, myalgia/arthralgia and fatigue were taken into consideration, the median time to alleviation of symptoms was 30.5 hours (95% CI 22.6-45.8) with sore throat taking the longest to resolve. The median time to resuming activities of daily living (ADLs) was 103.0 hours (95% CI 94.9 hours- 119.6 hours) and ranged from 54.7 hours to 126.8 hours in the consecutive age brackets.

Adverse events were experienced by 62.4% of subjects. In the various age brackets (28 days to < 2 years, 2 to < 6 years, 6 to < 12 years, and 12 to < 16 years of age) the incidence for AEs ranged from 54.1 to 75% and tended to be higher for patients under 12 years. No deaths occurred but 2 subjects experienced serious adverse events (SAEs): influenzal pneumonia in one and pneumonia and encephalopathy in the other. Both children recovered. Most AEs were mild to moderate (79.5%). Overall, the most frequent TEAEs were decreased neutrophil count (21.4%), diarrhea (16.2%), vomiting (9.4%), and increased eosinophil count (7.7%). Of note, there were 3 subjects (2.6%) who experienced abnormal behavior.

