- Doses of antipyretic medication and any medications taken for symptomatic relief, each day through the last follow-up assessment.

- The ability of the child or adolescent to return to day care/school and/or resume their normal "pre-illness" daily activity will be assessed once daily until the child or adolescent returns to day care/school and/or resume normal "pre-illness" daily activity.
- The child or adolescent's appetite and eating patterns assessed as normal or reduced/abnormal will be assessed once daily until they return to normal "pre-illness" level.

All parents/caregivers of subjects 7 years of age and older will record the following additional information in the Subject Diary:

• Assessment of 7 influenza symptoms (cough, sore throat, nasal obstruction, myalgia [muscle aches), headache, feverishness, and fatigue) on a 4-point severity scale (0, absent; 1, mild; 2, moderate; 3, severe) twice daily, beginning pre-dose on Day 1 until symptom resolution or through the last follow-up visit, (whichever comes first).

All parents/caregivers of subjects ≥ 4 years of age to ≤ 6 years of age will record the following additional information in the Subject Diary:

• Assessment of 7 influenza symptoms [cough, sore throat, nasal obstruction, myalgia (muscle aches), headache, feverishness, fatigue/malaise, and gastrointestinal symptoms (nausea, vomiting or diarrhea)] on a 4-point severity scale (0, absent; 1, mild; 2, moderate; 3, severe) twice daily, beginning pre-dose on Day 1 until symptom resolution or through the last follow-up visit, whichever comes first.

All parents/caregivers of subjects \le 3 years of age will record the following additional information in the Subject Diary:

• Assessment of 5 influenza symptoms [cough, rhinitis, feverishness, malaise/irritability and gastrointestinal symptoms (nausea, vomiting or diarrhea)] on a 4-point severity scale (0, absent; 1, mild; 2, moderate; 3, severe) twice daily, beginning pre-dose on Day 1 until symptom resolution or through the last follow-up visit, (whichever comes first).

An adequate nasal swab specimen will be collected from all enrolled subjects at Baseline (pre-dose) for virus sub-type identification and quantitative virologic assessments and at the follow-up assessments on study Days 3, 7, and where possible Day 14.

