10.3.3. Assessment of ability to perform usual daily activities

If possible, subjects or parents/care givers will be asked to provide a daily assessment of the subject's ability to perform usual daily activities using a 0-10 visual analogue scale, where 0 = Unable to perform usual activities at all, and 10 = Able to perform usual activities fully. The parent/care giver will be asked to record these assessments in the Subject Diary, with appropriate input from the subjects, once daily from Day 2 until resolution or the final follow-up assessment, whichever comes first.

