#### 4.3.4. Missing Data and Outliers

Every effort will be made to obtain required data at each scheduled evaluation from all subjects who have been randomized. No attempt will be made retrospectively to obtain missing subject reported data (such as influenza symptom severity assessments, temperature, and injection site discomfort) that has not been completed by the subject at the time of return of the subject diary to the investigative site. In situations where it is not possible to obtain all data, it may be necessary to impute missing data, as described in the following paragraph.

In assessing the effectiveness endpoint of time to alleviation of symptoms, for subjects who withdraw or who do not experience alleviation of symptoms, missing data will be censored using the date of subject's last non-missing assessment of influenza symptoms. Missing assessments of influenza symptoms will be imputed using the last observation carried forward. For the subject diary data, the following data conventions will be utilized. Missing diary completion times will be imputed as 11:59 for diary entries designated as morning and 23:59 for evening and daily reported values. Entries with values exceeding the 24-hour clock will be handled on a case-by-case basis and reviewed by a member of the clinical project team prior to implementation. In general, values recorded between 24:01 – 24:59 will be interpreted as values past midnight and will be implemented as such. Values recorded as 60:00, 70:00, and 80:00 will be interpreted as 06:00, 07:00, and 08:00, respectively. Should additional data conventions be required, these will be documented in the derived variable specifications and in the final clinical study report. Select exploratory sensitivity analyses may be conducted to ascertain the effect, if any, of these methods. These sensitivity analyses are further described in section 6.2.2.1. Other secondary effectiveness endpoints with time to event data will be censored using the date of subject's last non-missing assessment of the given endpoint.

Unless otherwise specified, no other missing data will be imputed.

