The development of any post treatment genotypic changes in neuraminidase and hemagglutinin will be assessed by comparison of sequences from baseline and last positive post-treatment virus samples. These analyses will be presented overall and by age group, treatment group and viral subtype.

The number and percentage of subjects experiencing influenza related complications will be summarized by age group and overall by complication preferred term and treatment group.

The number of doses of antipyretic medications, as recorded in the subject diary, taken throughout the study and by study day will be summarized by age group and overall by treatment group.

The change in daily activities will be summarized each day by treatment group for each age group and overall.

The shift in the assessment of appetite and eating patterns from baseline to each day will be summarized by treatment group for each age group and overall.

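### Daily activity and appetite summaries progressively lose children who have recovered, because recording stops on recovery and the SAP has no rule for the days that follow

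*SAP*

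**What the plan says.** **Planned analysis.** SAP 6.2.1 lists daily activities and appetite among the effectiveness endpoints. SAP 6.2.2 says of activity that "The change in daily activities will be summarized each day by treatment group for each age group and overall", and of appetite that "The shift in the assessment of appetite and eating patterns from baseline to each day will be summarized by treatment group". Tables 14.2.6 and 14.2.7 report them in the ITTI population.

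**Recording rule.** Protocol 10.1 says that activity "will be assessed once daily until the child or adolescent returns to day care/school and/or resume normal" function, and that appetite "will be assessed once daily until they return to normal". Protocol 10.3.3 has the 0-10 activity scale recorded "once daily from Day 2 until resolution or the final follow-up assessment, whichever comes first", and 10.3.4 gives the same rule for appetite. Footnote 10 to the visit schedule (Protocol Table 1, repeated in SAP 2.2) uses a different trigger: both items are recorded until every influenza symptom has cleared.

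**Missing data.** SAP 4.3.4 carries the last observation forward for influenza symptoms. It then says "Unless otherwise specified, no other missing data will be imputed".

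**Denominators.** SAP section 9 takes the sample size of a continuous summary as the count of observed values. Category percentages are taken over the total in that module.

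**Visits.** Protocol 10.2.2.3 to 10.2.2.5 list both items at Days 3, 7 and 14 with no condition on recovery. A Day 14 visit held by telephone collects neither.

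**The concern.** The blanks after recovery are not accidental. They arise by design because the child is well, so whether a value exists depends on the outcome being summarized. A table built from observed values then reports, on days without a visit, children who had not recovered before that day. It does not report the state of the treatment group.

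A reader of Tables 14.2.6 and 14.2.7 would see slow or flat recovery between visits and possible jumps on visit days. The group that recovers faster also loses its recovered children sooner, so a real difference between treatment or age groups can be muted. Description is the only analysis these endpoints receive, so no other result would correct the impression.

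**Working it through.** The plan gives no figure to reproduce here. The check first follows the rules through and then illustrates the size.

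**Step 1: the rules together.** A child whose appetite returns to normal on Day 4 records that on Day 4 and then stops (Protocol 10.1 and 10.3.4). Day 5 has no value. SAP 4.3.4 supplies none, because its carry-forward covers symptoms only. SAP section 9 then drops the child from the Day 5 percentage. If the Day 7 visit records the item, the child returns for that day. No time-to-event analysis of activity or appetite is planned that would use the recovery date.

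**Step 2: inputs for an illustration.** The documents give no recovery curve for this trial. Protocol 5.3.2.1 reports for an earlier pediatric study that "The median time to resuming activities of daily living (ADLs) was 103.0 hours", ranging from 54.7 to 126.8 hours across age brackets. Assumptions: an exponential curve, the first normal entry is the last one, no visit-day records, and the same curve for appetite.

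With median m and F(t) = 1 - 2^(-t/m):
- Recovered by the end of day d: F(24d).
- Still recording at the start of day d: 1 - F(24(d-1)).
- Normal among those recording on day d: [F(24d) - F(24(d-1))] / [1 - F(24(d-1))].

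**Step 3: results for m = 103 h.**
- Day 6 recovered: 1 - 2^(-144/103) = 62%. Still recording: 2^(-120/103) = 45%. Normal among recorders: 1 - 2^(-24/103) = 15%.
- Day 11 recovered: 1 - 2^(-264/103) = 83%. Normal among recorders: again 15%, since the exponential hazard is constant.
- With a log-normal curve (same median, assumed sigma 0.6), recovered versus normal among recorders is 71% versus 28% on Day 6 and 94% versus 26% on Day 11.

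**Step 4: two groups, with medians at the ends of the quoted range (54.7 and 126.8 h), Day 6, exponential.**
- Recovered: 1 - 2^(-144/54.7) = 84% versus 1 - 2^(-144/126.8) = 54%.
- Normal among recorders: 1 - 2^(-24/54.7) = 26% versus 1 - 2^(-24/126.8) = 12%. A gap of about 29 points (83.9% - 54.5%) shrinks to about 14.
- Log-normal (sigma 0.6), normal among recorders: 44% versus 22% on Day 6 and 37% versus 23% on Day 11. The order of the groups is kept.

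For the activity scale, assume a baseline of 2, a mean of 5 while unrecovered and 10 once recovered. Mean change is then 3 + 5 x (share recovered).
- All children: 3 + 5(0.839) = 7.2 versus 3 + 5(0.545) = 5.7, a difference of 1.5.
- Recorders, counting the recovery-day entry: 3 + 5(0.262) = 4.3 versus 3 + 5(0.123) = 3.6, a difference of 0.7.
- Recorders not recovered before Day 6, without recovery-day entries: +3.0 in both groups, so no difference. This follows directly from assuming the same mean of 5 in both groups.

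**The case against.** **The stopping trigger is not uniform.** Under footnote 10, the only stop rule the SAP itself gives for these items, a child with normal activity and appetite but a lingering mild cough keeps recording. That child stays in the denominator, and the formulas above do not apply. This stands as a limit on the size. Loss linked to recovery remains under that trigger too, but the documents do not allow it to be measured.

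**Recovered children are not wholly absent.** A reader might infer that the tables describe only children who are still ill. The documents do not support that. The entry on the day of recovery counts, and the visits on Days 3, 7 and in-person Day 14 may record every child. How complete those visits are is unclear, because footnote 10 attaches its stop rule to the same schedule row and a telephone Day 14 omits both items.

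**Reversal is not shown.** A reader might also infer that a group difference could change sign. In both recovery models the faster group keeps the higher share of normal entries among recorders. Attenuation is shown. Complete masking on the activity scale needs the added assumption of equal means while unrecovered and the exclusion of recovery-day entries.

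**The consequence is bounded.** No hypothesis is tested (Protocol 13.3), and neither item is among the secondary endpoints in Protocol 7.1.2. SAP section 9 requires the contributing n to be shown, so the shrinking count would be visible. Symptom alleviation and fever resolution have Kaplan-Meier analyses. All of this stands and keeps the point below a major one. A visible n shows that children are missing but does not tell the reader that they are missing because they recovered.

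**Conclusion.** The point holds. Followed as written, the SAP produces daily activity and appetite summaries whose denominators depend on the outcome. On non-visit days they increasingly exclude children who have already recovered, while visit days may include them. The series therefore understates recovery and can mask differences between groups.

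The direction follows from the text. The size does not: 62% recovered against 15% normal among recorders on Day 6 is illustrative. It rests on an assumed exponential shape, a median for resuming activities taken from an uncontrolled Japanese study, use of that median for appetite as well, and recording that ends at the first normal entry.

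The impact is modest, since these are descriptive SAP effectiveness endpoints. The change is still worth making because it is cheap and the tables would otherwise mislead.

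**What to change.** First reconcile the stopping triggers: recovery of the item in Protocol 10.1, 10.3.3 and 10.3.4, against clearance of all symptoms in footnote 10 of both documents. State what counts as normal for each item. The and/or in the Protocol 10.1 activity trigger means that recording can stop without a score of 10, and under footnote 10 it could stop with appetite still reduced.

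Then amend SAP 4.3.4 and 6.2.2 in one of two ways:

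- **(a) Carry forward documented recovery.** Once the diary documents return to normal and recording stops under the protocol, carry forward the last documented recovered value until a later assessment shows otherwise. Do not insert an assumed 10. Keep this state distinct from dropout and missing diaries. Present the proportion recovered by day over all ITTI subjects, with the number actually recorded each day.
- **(b) Replace the daily summaries** with Kaplan-Meier time to normal activity and time to normal appetite, censored at the last record.

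The cost is wording, to settle the triggers and amend the SAP, plus derivation programming. No new data are needed. The downside is that a relapse between visits that nobody recorded would be missed.

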# **6.2.3.** Exploratory Exposure Response Analyses

Summaries of plasma concentrations will be presented by time point, age group, and treatment group. Scatter plots will be generated for time to alleviation of influenza symptoms and change from baseline in  $\log_{10} \text{ TCID}_{50}/\text{mL}$  versus peramivir plasma concentration at 30-60 minutes following study drug administration. The data from this trial together with data from prior trials will be used to complete a separate exposure-response analysis. The methods for the exposure-response analysis will be presented in a separate SAP.

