7. INVESTIGATIONAL PLAN

7.1. Endpoints

7.1.1. Primary Endpoint

The primary endpoints of this study will be assessment of adverse events, laboratory analyses (clinical chemistry, hematology and urinalysis), vital signs and physical examinations.

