7.2. Overall Study Design and Plan

This is a multi-center, open label active-controlled study to evaluate the safety, pharmacokinetics and effectiveness of IV peramivir in children.

Up to 140 subjects will be enrolled in this study according to the following age groups:

- Birth to < 28 days: up to 10 subjects will receive IV peramivir
- 28 days < 2 years: up to 20 subjects: subjects enrolled after the approval of amendment 3 will receive IV peramivir
- 2 <4 years: up to 10 subjects: subjects enrolled after the approval of amendment 3 will receive IV peramivir
- 4 < 7 years:up to 30 subjects: subjects enrolled after the approval of amendment 3 will receive IV peramivir
- 7 < 13 years:up to 40 subjects, randomized 4:1 to IV peramivir or oral oseltamivir
- 13 < 18 years:up to 30 subjects, randomized 4:1 to IV peramivir or oral oseltamivir

Once an age cohort is filled, enrollment in that cohort will be closed and communicated with all investigators.

A subject's duration of participation in this study is expected to be 14 days.

All subjects will receive either a single dose of IV peramivir (600 mg IV for subjects \geq 13 years, 12 mg/kg IV for subjects \geq 6 months - \leq 12 years, 8 mg/kg for subjects \leq 6 months IV) or oral oseltamivir, dosed BID for 5 days.

Note, as of the date of amendment 3, no additional subjects will be randomized to receive oseltamivir.

Subjects will undergo follow-up assessments on Days 3, 7, and 14. The Day 3 visit may be a home visit (performed by a qualified study nurse). Day 7 is required to take place in the clinic, and Day 14 may either be a clinic visit, home visit, or follow-up phone call to the subject/parent/guardian.

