9.2. Treatments Administered

9.2.1. Peramivir

Peramivir solution for infusion is a clear, iso-osmotic, sterile, nonpyrogenic solution in 200 mg per 20 mL (10 mg/mL) single-use glass vials fitted with rubber stoppers and aluminum flip-off seals. The drug product should be stored at room temperatures up to 30°C.

Subjects < 6 months of age at time of consent will receive a single dose of IV peramivir at a dose of 8 mg/kg. Subjects ≥ 6 months $- \le 12$ years of age at time of consent will receive a single dose of IV peramivir at a dose of 12 mg/kg (up to a maximum dose of 600 mg). Subjects ≥ 13 years of age will receive a single dose of 600 mg IV peramivir administered as a short IV infusion over a minimum of 15 minutes. Peramivir must be diluted in normal saline normal saline United States Pharmacopeia (SUP).:

Because of the risk of vasovagal reactions, particularly in children with needle phobia, it is recommended that subjects be in a supine position during peramivir administration. Appropriate post infusion observation should be performed.

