13. STATISTICS

Descriptive statistical methods will be used to summarize the data from this study. Data will be summarized by treatment group, age group, and study day/time, if appropriate. Unless stated otherwise, the term "descriptive statistics" refers to number of subjects (n), mean, median, standard deviation (SD), minimum, and maximum for continuous data and frequencies and percentages for categorical data. The term "treatment group" refers to treatment assignment: single dose peramivir IV or oseltamivir BID for 5 days. The term "age group" refers to the following: 0-28 days; 28 days -<2 years, ≥ 2 years -<7 years, ≥ 7 years -<13 years, and ≥ 13 years -<18 years. All data collected during the study will be included in data listings. Unless otherwise noted, the data will be sorted first by treatment group, age group, subject number, and then by date within each subject number.

The statistical analyses will be conducted with the SAS® software package version 9.2 or higher. All analyses will be subject to formal verification procedures. Specifically, results will be verified utilizing independent programming prior to issuance of the draft statistical report. All documents will be verified by the lead statistician to ensure accuracy and consistency of analyses.

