#### 4.3.8. Definitions and Terminology

#### Age

Age will be defined as the age in days for the cohort of subjects <28 days old, months for the cohort of subjects from 28 days - 2 years, or years for the cohorts of subjects greater than 2 years old at the time of randomization. For all subjects, age in years will also be derived and rounded down to the tenth decimal place for the summary statistics that are presented for all subjects combined.

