#### 6. STATISTICAL METHODS

Descriptive statistical methods will be used to summarize the data from this study. Data will be summarized by treatment group, age group, and study day/time, if appropriate. Unless stated otherwise, the term "descriptive statistics" refers to number of subjects (n), mean, median, standard deviation (SD), minimum, and maximum for continuous data and frequencies and percentages for categorical data. The term "treatment group" refers to randomized treatment assignment: single dose peramivir IV or oseltamivir BID for 5 days. The term "age group" refers to the following: 28 days - < 2 years,  $\ge$  2 years - < 7 years,  $\ge$  7 years - < 13 years, and  $\ge$  13 years - < 18 years. All data collected during the study will be included in data listings. Unless otherwise noted, the data will be sorted first by treatment group, age group, subject number, and then by date within each subject number.

The statistical analyses will be conducted with the SAS® software package version 9.2 or higher. All analyses will be subject to formal verification procedures. Specifically, results will be verified utilizing independent programming prior to issuance of the draft statistical report. All documents will be verified by the lead statistician to ensure accuracy and consistency of analyses.

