#### **6.3.3.** Clinical Laboratory Assessments

Descriptive summaries of the following selected (quantitative) clinical laboratory results will be presented by study visit and treatment group for each age group and overall: ALT, AST, Serum Creatinine, BUN, HGB, Albumin, and Alkaline Phosphatase. Laboratory abnormalities (toxicities) will be graded according to the DAIDS Table for Grading Adverse Events for Adults and Pediatrics (Publish Date: December 2004). The number and percentage of subjects experiencing treatment-emergent graded toxicities will be summarized by treatment group for each age group and overall. Laboratory toxicity shifts from baseline to Day 7 will be summarized by treatment group for each age group and overall.

All laboratory toxicities that occurred before the initiation of study treatment or more than 14 days post study drug discontinuation will be excluded from the tables but will be included in the listings.

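### The SAP was not updated to Protocol 6.0: newborns have no age row, non-randomized children fall outside its ITT and safety populations, and no age row shows the 8 mg/kg dose alone

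*SAP*

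**What the plan says.** **Age groups.** In Protocol 13 the term age group "refers to the following: 0-28 days; 28 days -<2 years", followed by three older groups, five in all. In SAP 6 it "refers to the following: 28 days - < 2 years", followed by the same three, four in all. The SAP does recognise the youngest cohort elsewhere. SAP 2.1 and 4.2 describe its enrolment, and SAP 4.3.8 says "Age will be defined as the age in days for the cohort of subjects <28 days old". Protocol 7.2 sizes it: "Birth to < 28 days: up to 10 subjects will receive IV peramivir".

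**Dose.** Protocol 9.2.1: "Subjects < 6 months of age at time of consent will receive a single dose of IV peramivir at a dose of 8 mg/kg". From 6 months through 12 years the dose is 12 mg/kg, capped at 600 mg. SAP 2.1 gives 12 mg/kg to the newborns, and also to the 28-day to <2-year cohort enrolled under protocol version 4.0 or later. The 8 mg/kg dose appears nowhere in the SAP.

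**Populations.** Under Protocol 9.3, every child under 7 receives peramivir once amendment 3 is approved. SAP 5.1 defines ITT as the randomized subjects, and SAP 5.3 defines safety as randomized subjects given at least a partial dose. Protocol 13.5 defines safety by receipt of study drug alone; its ITT definition still says randomized.

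**Tables.** Concentrations: "Summaries of plasma concentrations will be presented by time point, age group, and treatment group" (SAP 6.2.3). SAP 6.3.3 says selected laboratory results "will be presented by study visit and treatment group for each age group and overall". Protocol 13.9 summarises AEs by age group and treatment group; SAP 6.3.1 names treatment group only. In SAP 10, the by-time-point concentration table (14.4.1.1) uses the ITT population and the 14.3 series uses the safety population.

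**The concern.** Protocol 7.1.1 says "The primary endpoints of this study will be assessment of adverse events, laboratory analyses", among other safety measures, and Protocol 13.3 tests no hypothesis. The descriptive safety tables are therefore the planned primary result, not a supplement to one.

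The 8 mg/kg dose rests on simulations, which Protocol 5.4 says should give exposure similar to that in adults and in the children who had already completed the study. A reader will want observed concentrations and safety findings for the children who received that dose set beside the prediction. As the SAP stands, newborns have no row, the next row crosses the dose change at 6 months, and the population wording can exclude the non-randomized children altogether.

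A second feature makes the mixed row harder to read. Under Protocol Table 1 (footnote 15), children below 5 kg give two PK samples rather than four: at the end of infusion and at 1-3 hours. The blend of 8 and 12 mg/kg can then change from one time point to the next within the same row.

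**Working it through.** **1. Which rows hold which dose.** Cohort caps are from Protocol 7.2, doses from Protocol 9.2.1.

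| Age band | Cap | Row in Protocol 13 | Row in SAP 6 | Current peramivir dose |
|---|---|---|---|---|
| Birth to <28 days | 10 | yes | no | 8 mg/kg |
| 28 days to <2 years | 20 | yes | yes | 8 mg/kg below 6 months, 12 mg/kg from 6 months |
| 2 to <7 years | 10 + 30 = 40 | yes | yes | 12 mg/kg |
| 7 to <13 years | 40 | yes | yes | 12 mg/kg, maximum 600 mg |
| 13 to <18 years | 30 | yes | yes | 600 mg |

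The caps sum to the planned total: 10 + 20 + 40 + 40 + 30 = 140. SAP rows containing only 8 mg/kg: 0 of 4. Restoring the newborn row helps, but 8 mg/kg children aged 28 days to <6 months stay in a mixed row.

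**2. How mixed the infant row could be.** The number under 6 months among the 20 is not given. If k of 20 are, all receive peramivir and all follow the current rule, the mean dose is (8k + 12(20 - k))/20. For k = 0, 5, 10, 15, 20 this is 12, 11, 10, 9, 8 mg/kg.

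**3. What pooling does to a mean concentration.** Let s be the share under 6 months and r the ratio of their mean to the older infants' mean. Pooled mean / older mean = 1 + s(r - 1). Both inputs are assumptions.

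| r | s = 25% | s = 50% |
|---|---|---|
| 0.667 (proportional to mg/kg) | 0.917 | 0.833 |
| 1 (as the simulations predict) | 1.00 | 1.00 |
| 1.5 | 1.125 | 1.25 |

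Neither the sign nor the size can be settled from the documents.

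**4. Who drops out under the population wording.** All newborns (up to 10) are assigned, not randomized. So is an unstated part of the 20 + 10 + 30 = 60 places from 28 days to <7 years. The total is below 70 of 140, because the Protocol synopsis says the 2-7 year cohort was already partly enrolled under randomization. The 14.3 safety tables and Table 14.4.1.1 are affected. Table 14.4.1.2 and the effectiveness tables are not, because the ITTI definition (SAP 5.2) requires enrolment, treatment and RT-PCR confirmation but not randomization.

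**5. Cell sizes after a split.** With no event in n children, the one-sided 95% upper limit is 1 - 0.05^(1/n): 45% at n = 5, 26% at 10, 18% at 15, 14% at 20. A subtotal of 15-20 assumes 10 newborns plus 5-10 older infants, all at 8 mg/kg.

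**6. Protocol Table 3 (secondary).** Volume = kg x mg/kg / 10 mg/mL (stock strength from Protocol 9.2.1).
- 0 to <28 days: 3 kg gives 2.4 and 5.5 kg gives 4.4 mL; both match.
- 28 days to <3 months: 3 kg gives 2.4 and 7.5 kg gives 6.0 mL; both match.
- 3 to <6 months: 4.5 kg gives 3.6 mL (match); 11.2 x 8 / 10 = 8.96 mL, printed 4.7.
- 6 to <12 months: 4.5 x 12 / 10 = 5.4 mL, printed 7.2; 11.2 kg gives 13.44 mL (match).

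Six of eight endpoints reproduce. Working back, 4.7 x 10 / 8 = 5.9 kg and 7.2 x 10 / 12 = 6.0 kg. Assuming saline at 0.154 mEq/mL, sodium from the printed volumes is (25 - 4.7) x 0.154 = 3.13 and (25 - 7.2) x 0.154 = 2.74, matching the printed 3.1 and 2.7. From the printed weights it would be 2.47 and 3.02. Volumes and sodium agree with each other, so the repeated weight band is the likelier misprint.

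**The case against.** The strongest reply is that the SAP has simply been overtaken. Its page footer (at SAP 6.2.4) is dated 11 July 2016, its one logged revision is from June 2016, and the protocol version it cites is 4.0 or higher. On its own terms every infant gets 12 mg/kg and no row crosses a dose change. That explains the cause and makes the remedy an update rather than a redesign. It does not close the gap against Protocol 6.0.

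A reader might infer that the newborns were dropped on purpose. The documents do not support this. SAP 7 declares one added analysis and no other change, and three other SAP sections keep the cohort, so an incomplete list is the better explanation. The list is nevertheless the definition the tables will follow.

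It is also fair that 28 days to <2 years is a prespecified group in both documents. Exposure is assigned mainly to population PK modelling with a renal maturation factor, and subject-level listings are planned. This largely stands: 8 mg/kg exposure does not go unexamined. But PK modelling does not summarise AEs or laboratory results. The listings are also described inconsistently: SAP 5 includes all enrolled subjects, SAP 9 only those randomized.

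Finally, a dose row would not separate dose from age, because under the current rule both change at 6 months. That stands in full.

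**Conclusion.** The concern holds as an updating failure with practical consequences for descriptive tables. Read literally, up to 10 newborns have no age row. An unstated number of non-randomized children (fewer than 70) leave the safety tables and the by-time-point concentration table. No SAP age row shows 8 mg/kg alone. For safety, the SAP population also conflicts with Protocol 13.5. It is worth correcting before the tables are programmed.

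Three stronger readings are tempting and unsupported:
- That age identifies the 8 mg/kg children. SAP 2.1 planned 12 mg/kg for both youngest cohorts, so some infants under 6 months may have received it. The documents do not show whether any did.
- That the pooled row is biased in a known direction. The 0.83 to 1.25 range comes entirely from assumed shares and ratios, and it is 1.00 if exposure is as predicted.
- That Table 3 causes misdosing. Dose is set in mg/kg, the volumes are labelled approximate, both disputed rows dilute to 25 mL, and preparation follows a separate Pharmacy Manual. The table is internally inconsistent, and that is all that is shown.

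**What to change.** 1. Add birth to <28 days to the SAP 6 age groups, as in Protocol 13.
2. Define the safety population as all subjects who received any study drug, and ITT as all randomized or assigned subjects. The ITT change also departs from the wording of Protocol 13.5, so record it in SAP 7. Align the treatment-group definition in SAP 6 and the listings rule in SAP 9. Take age at consent, since assigned children have no randomization date (SAP 4.3.8).
3. In the concentration, laboratory and AE tables, split the 28-day to <2-year peramivir row by mg/kg actually received (8 or 12) and add an all-8 mg/kg subtotal. Use age at consent (below 6 months or older) as the divider only if dosing records show that it matches dose received.
4. Update SAP 2.1 to the Protocol 6.0 doses.
5. Secondary: have the sponsor reconcile weights, volumes and sodium in Protocol Table 3 against the Pharmacy Manual.

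The cost is one added age group, one row split with a subtotal, and text corrections; no new data are needed. The downside is small cells. The subtotal eases this, but even at 15-20 children an event rate of 14-18% remains compatible with seeing none, so the rows should be read as description.
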